8.0 Data and Specimen Banking For Future Undetermined Research

- 8.1 Data and/or specimens being stored Not Applicable
- 8.2 Location of storage Not Applicable
- 8.3 Duration of storage Not Applicable
- 8.4 Access to data and/or specimens Not Applicable
- 8.5 **Procedures to release data or specimens** Not Applicable
- 8.6 Process for returning results Not Applicable

9.0 Statistical Plan

9.1 Sample size determination

874 is the maximum number of patient participants to be enrolled. The number of participants that will be contacted (874) is much larger than the number we intend to enroll (227). Based on the response rate of the first cohort in Spring 2016, we are confident that the recruitment process explained above will yield the required number of participants within the proposed period.

27 participants were enrolled during the first cohort in 2016.

9.2 Statistical methods

We will utilize a number of statistical methods. For example, basic t-tests and regression will be used for preliminary analyses. The majority of the analyses will center on two types: 1) moderated multiple linear regression (SEM models) for Aim 2 and 2) Mixed ANOVA for Aims 1 and 2.

10.0 Confidentiality, Privacy and Data Management

10.1 Confidentiality

The collected research data will be kept completely confidential. All hard copies of completed questionnaires will be labeled with a code number only (PIN) and stored in locked filing cabinets in locked offices. Survey responses will be entered into a secure research database: REDCap (Research Electronic Data Capture) is a secure, web-based application designed to support data capture for research studies. REDCap is maintained by the REDCap Consortium which is comprised of over 600 institutional partners including Penn State University, on a password protected computer in a locked office and/or the PRO Health Lab's departmental Penn State PASS drive, only accessible by the team members listed on this application.

We have taken the following steps to protect individuals' identities as research participants: 1) PSU research team will not have access to potential participants until they are pre-screened by Hershey staff and agree to participate or contact us directly via phone or email, and only the PSHMC Dermatology research nurse coordinator and Hershey team, who has access to this population, will be involved in the initial recruitment; 2) Responses to surveys will be identified only by a unique personal identifier (PIN), which is a number randomly generated for each participant in this study; 3) Hershey will keep a master list of names, addresses, phone numbers, and PINs so that they can mail recruitment letters, and PSU will create a master list based on the participants who agree to participate when pre-screened (and verbally consented) over the phone or contact us directly, to send reminder letters, 1-month and 3-month follow-up surveys and compensation. The master list of consented participants will be stored separately from the survey responses on a password protected computer in a locked office and/or the PRO Health Lab's departmental Penn State PASS drive, only accessible by the team members listed on this application; and all audio recordings will be destroyed once they are scored and coded.

Considering that participants will be sent a link and PIN number to access the 1-month, and 3-month follow-up surveys, they can complete it in any location they wish (e.g., home). The level of privacy they receive is limited to the location they choose to complete it at.

10.1.1 Identifiers associated with data and/or specimens

The data is de-identified as we use a PIN number to identify the data. Any identifiable information is used only to invite participants for follow-up surveys (and is marked as an identifier within REDCap) and to compensate them for participating in the study, and is stored in a file separate from the survey data.

10.1.1.1 Use of Codes, Master List

A master list containing a code number (PIN) and participants' identity will be stored in a separate password protected computer file within the REDCap database, only accessible by the study staff listed on this document. The overall list of ALL participants invited to the study will be maintained by the Hershey team; the Penn State team will keep a separate list as participants complete phone screening. This file will be kept separate from any collected data. The list will be saved on a password protected computer in a locked office and/or the PRO Health Lab's departmental Penn State PASS drive, only accessible by the team members listed on this application

10.1.2 Storage of Data and/or Specimens

All data will be stored in the REDCap database on locked, password protected computers in the PSHMC Dermatology Research office and PRO Health Lab ([name]) and/or on the PRO Health Lab's departmental Penn State PASS drive, only accessible by the team members listed

on this application. The data files may also be stored on a Penn State Project Box account accessible only by the individuals listed on this document. All data files will be void of any participant information, and data will be organized by randomly assigned ID numbers.

This study has been issued a Certificate of Confidentiality. Researchers will not disclose or provide any identifiable information without the subject's prior consent or where permitted according to NIH's Policy on Issuing Certificates of Confidentiality.

10.1.3 Access to Data and/or Specimens

Only the study staff listed on this application will have access to the list.

10.1.4 Transferring Data and/or Specimens

Data will be physically transported from the Penn State Hershey Medical Center clinic sites to PSU at University Park. Signed informed consents, baseline surveys, and audio recordings will be transported via vehicle from Penn State Hershey Medical Center clinic sites to PSU at University Park. The items will be transported in a locked file box in a locked car trunk.

10.2 Privacy

All data and other information in this study will be maintained confidentially, and will be identified only by a unique personal identifier (PIN), which is a number randomly generated for each participant. Data will be entered into an electronic, password protected file, only accessible by the study staff listed on this document. Considering that participants will be sent a link and PIN number to access the 1-month and 3-month follow-up surveys, they can complete it in any location they wish (e.g., home). The level of privacy they receive is limited to the location they choose to complete it.

11.0 Data and Safety Monitoring Plan

- **11.1 Periodic evaluation of data** Not Applicable
- **11.2 Data that are reviewed** Not Applicable
- **11.3 Method of collection of safety information** Not Applicable
- **11.4 Frequency of data collection** Not applicable
- **11.5** Individual's reviewing the data Not Applicable
- **11.6 Frequency of review of cumulative data** Not Applicable
- **11.7 Statistical tests** Not Applicable
- **11.8 Suspension of research** Not Applicable

12.0 Risks

Psychological risks posed by the research are primarily related to the sensitivity of some of the measures. Items include thoughts, feelings, and personal difficulties that may be private, and personal behavior such as thinking about their likelihood of developing skin cancer. These questions may make participants uncomfortable, or be perceived as an intrusion on their privacy. Although it is our responsibility to point out the potential for these risks, we must emphasize that we have not observed any indications of these risks materializing in any of our previous research using the same procedures we will employ in this study. Participants will be assured of their voluntary participation in the study, their choice to answer or not answer any question, and of our protocol for maintaining confidentiality.

We have taken steps to protect participants against potential risks posed by their participation in this research. Psychological risks of invasion of privacy or increased awareness or concern about one's behavior as a result of completing the assessments will be addressed as a risk in the consent form. Participants are encouraged to contact the investigators at any time to discuss any concerns they might have. Drs. [name] (PI) and [name] (Co-Investigator) are qualified to provide referrals and address concerns related to psychological distress arising through participation.

Additionally, we have a Certificate of Confidentiality from NIH.

13.0 Potential Benefits to Subjects and Others

13.1 Potential Benefits to Subjects

Through completing this questionnaire, participants may become more aware of their skin protective behaviors and risk factors, which may prompt some behavior change. However, there may be no direct benefit to participants.

13.2 Potential Benefits to Others

The knowledge to be gained from this study is of great importance and will benefit others and society as a whole. Findings will help to improve physician-patient communication, to increase the use of sun-protective behaviors, and therefore reduce the chance of developing skin cancer among patients.

14.0 Sharing Results with Subjects

Not Applicable

15.0 Economic Burden to Subjects

15.1 Costs

The participant will not bear any costs.

15.2 Compensation for research-related injury

Not Applicable – the research does not involve more than minimal risk to subjects.

16.0 Number of Subjects

The total maximum number of participants to be enrolled is 894.

The number of patient participants that will be contacted (up to 874) is much larger than the number we intend to enroll (227 – including both Cohort 1 and Cohort 2) (27 enrolled in Cohort 1 between Intervention and Control; 200 intended to enroll in Cohort 2 – 100 intervention, and 100 control). Based on the response rate of the first cohort in Spring 2016, we anticipate a 26% overall response rate, resulting in 200 individuals (for cohort 2) who agree to participate. However, due to uncertainty on the

overall response rate, participants will be invited in chunks and once we hit our target enrollment, we will stop recruiting. Additionally, we will enroll up to 20 providers (up to 10 from the control site and up to 10 from the intervention site).

17.2 Feasibility of recruiting the required number of subjects

We have access to all dermatology patients at both the intervention and control sites. We have secured agreement to use both clinics. Out of all of the dermatology patients, we will only be recruiting a portion.

17.3 PI Time devoted to conducting the research

Given the current research load and the quality and size of the research support team, there is no doubt the PI will have sufficient time to conduct the proposed research.

17.4 Availability of medical or psychological resources

Participants are encouraged to contact the investigators at any time to discuss any concerns they might have. Drs. [name] (PI) and [name] (Co-Investigator) are qualified to provide referrals and address concerns related to psychological distress arising through participation.

17.5 Process for informing Study Team

All members of the research staff will be sufficiently trained in study procedures, protocol, and timeline. They will be reminded of confidentiality procedures. Each staff member will receive a copy of the original grant proposal and the approved IRB application. We will walk through procedures in person. Study staff who will be on site at the clinics for consenting participants, administering surveys, and audio recording participants, will be trained on the proper procedures.

18.0 Other Approvals

This project is funded by the National Cancer Institute/National Institutes of Health, and we have a Certificate of Confidentiality as well.

19.0 Subject Stipend (Compensation) and/or Travel Reimbursements

All patient participants will be compensated for their participation in the study. Patients will receive \$25 for completing each of the 3 surveys (baseline, 1-month, and 3-month follow-up). The compensation for the baseline survey will be dispersed at the clinic after completing the baseline survey. The compensation for the two follow-up surveys will be dispersed at the end of the study (that is, after the 3-month follow-up). Participants may choose to receive either a Walmart gift card, a Target gift card, or an Amazon electronic gift card. The total possible compensation is \$75. If a participant does not complete the study in its entirety (that is, they completed some but not all of the surveys), they will be paid for the surveys that they completed.

20.0 Multi-Site Research

- 20.1 Communication Plans Not Applicable
- 20.2 Data Submission and Security Plan Not Applicable
- 20.3 Subject Enrollment Not Applicable
- 20.4 Reporting of Adverse Events and New Information Not Applicable
- 20.5 Audit and Monitoring Plans Not Applicable

21.0 Adverse Event Reporting

21.1 Reporting Adverse Reactions and Unanticipated Problems to the Responsible IRB

In accordance with applicable policies of The Pennsylvania State University Institutional Review Board (IRB), the investigator will report, to the IRB, any observed or reported harm (adverse event) experienced by a subject or other individual, which in the opinion of the investigator is determined to be (1) unexpected; and (2) probably related to the research procedures. Harms (adverse events) will be submitted to the IRB in accordance with the IRB policies and procedures.

21.2 Auditing and Inspecting

The investigator will permit study-related monitoring, audits, and inspections by the Penn State quality assurance program office(s), IRB, the sponsor, and government regulatory bodies, of all study related documents (e.g., source documents, regulatory documents, data collection instruments, study data etc.). The investigator will ensure the capability for inspections of applicable study-related facilities (e.g., pharmacy, diagnostic laboratory, etc.).

22.0 Study Monitoring, Auditing and Inspecting

22.1 Auditing and Inspecting

The investigator will permit study-related monitoring, audits, and inspections by the Penn State quality assurance program office(s), IRB, the sponsor, and government regulatory bodies, of all study related documents (e.g., source documents, regulatory documents, data collection instruments, study data etc.). The investigator will ensure the capability for inspections of applicable study-related facilities (e.g., pharmacy, diagnostic laboratory, etc.).

24.0 Appendix

25.0 Statistical Analysis Plan

25.1 Power/Sample Sizes

The sample sizes were chosen based on statistical, analytic, and theoretical considerations. For comparisons of the ABC vs. TAU controls on our outcome variables for Aim 1 (e.g., sun protection behaviors), our N should be able to detect effect sizes that correspond to small effects, Cohen's d = .2 or eta squares of 2%. The effect sizes are based on our pilot study examining patients' sunscreen use intentions following exposure to the ABC intervention (see preliminary studies section) and our studies examining group differences using motivational enhanced interventions to reduce tanning intentions and behaviors. Using power estimation procedures described in Cohen, the sample sizes should vield power of greater than 0.90 for the contrasts of interest. A second analysis that we will pursue will be moderated multiple linear regression or SEM models for Aim 2. [name] has special expertise in such analyses, where we test for effectiveness of the intervention as a function of a moderator variable at baseline (e.g., gender). With every moderator, our sample sizes for each group are reduced by approximately 50%. With our target N = 300 (at baseline), we will have sufficient samples to explore the potential of 2 moderators simultaneously and still have sample sizes that approximate n = 37 per group. Such Ns will also permit us to detect partial r2 sizes in the .04-.06 range and will have power of .70 or greater for the contrasts of interest.

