- 3) For those who are called and invited to participate over the phone by a PSHMC research assistant, the research assistant will explain the study, and if the patient is interested, the research assistant will obtain verbal consent to screen patients to see if they qualify for the study based on the inclusion/exclusion criteria. If they are eligible, they will then be formally invited. Potential participants interested in the study will be asked to arrive 25 minutes early for their appointment so that the consent form may be reviewed with them in its entirety and signed informed consent can be obtained in a private area of the clinic prior to the completion of the brief baseline survey. A log will be kept of all de-identified patients contacted via phone who declined participate when approached in the clinic (example: adult male #1 refused study due to time commitment).
- 4) In the first cohort in Spring 2016, we enrolled 27 participants who qualified after completing the screening. For the second cohort in Spring 2017, we plan to enroll an additional sample of 200 (100 per site). Based on the response rate of the first cohort in Spring 2016, we will invite up to 770 participants in Spring 2017. Once the target enrollment of 200 total (about 100 per site) is obtained, we will discontinue recruiting. The study will be split into 2 cohorts

– one taking place in Spring 2016 (n=27) and the other taking place in Spring 2017 (target n=200).

- 5) Participants who are interested and who qualify to participate will either: 1) be asked on the phone for their email address in order to send a copy of the consent form and reminder to arrive at their scheduled appointment 25 minutes prior to their scheduled time, or 2) receive a copy of the informed consent and a letter by mail reminding them to arrive at their scheduled appointment 25 minutes before their scheduled time to perform the written informed consent process and to complete the baseline survey. Participants will also be called 1-3 days before their scheduled appointment to remind them to arrive 25 minutes early (see reminder phone script).

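### Section 25.1 is built on 300 patients although 227 will be enrolled, and its power above 0.90 is not reached for the Group main effect when d = .2 is the between-group difference

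*Combined protocol and SAP*

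**What the plan says.** Section 25.1 states for the Aim 1 comparison that "our N should be able to detect effect sizes that correspond to small effects, Cohen's d = .2 or eta squares of 2" per cent, and that "the sample sizes should vield power of greater than 0.90 for the contrasts of interest". It refers to power procedures in Cohen. It names no test, alpha, within-person correlation or allowance for attrition.

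The sample size appears later in the same section, in the discussion of Aim 2: "With our target N = 300 (at baseline"), with two moderators examined together and "still have sample sizes that approximate n = 37 per group".

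Elsewhere the target is smaller. Section 9.1 says the number contacted "is much larger than the number we intend to enroll (227"). Section 16.0 breaks this down: "27 enrolled in Cohort 1 between Intervention and Control; 200 intended to enroll in Cohort 2". Section 4.2 gives the stopping rule for the second cohort: "Once the target enrollment of 200 total (about 100 per site) is obtained, we will discontinue recruiting".

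Section 25.3 supplies the Aim 1 analysis, a 2 x 3 mixed ANOVA (Group by Time). It expects a Group main effect, and a Group x Time interaction with no baseline difference and a difference at each follow-up. Section 9.2 gives simple two-group tests a minor role: "basic t-tests and regression will be used for preliminary analyses". Section 25.3 also sets a meaningfulness rule: an observed effect below d = .20 is deemed nonsignificant even if the null is rejected.

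**The concern.** Two things do not fit. First, the N and cell size in section 25.1 are not those of the study described in sections 4.2, 9.1 and 16.0, and no section reconciles them. Second, power above 0.90 for a difference of d = .2 is far more than 227 or 300 patients normally provide, and the section does not give the inputs needed to check it.

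Section 1.1 presents the study as a preliminary analysis ahead of a large randomised trial. A non-significant result will be read against the power figure. A reader who believes the study had better than 90% power for d = .2 would take a null result as strong evidence against the intervention. Patient treatment and follow-up are not affected.

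**Working it through.** **Inputs from the documents.** N = 300 (section 25.1) and N = 227 (sections 9.1 and 16.0); d = .2 or eta squared 2% (section 25.1); Group and Group x Time in a 2 x 3 mixed ANOVA (section 25.3).

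**Assumptions.** Two-sided .05 (section 25.4 gives .05 only for the mediation paths), equal groups, no loss, independent patients, and one common within-person correlation r ≥ 0, with .3 to .8 as the working range. Pairs below are N = 300 / N = 227. Power is from the noncentral F with noncentrality L.

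**1. Sample size.** Two groups and two binary moderators make 8 cells. 300/8 = 37.5, which reproduces the stated 37. The enrolment target is 27 + 200 = 227, and 227/8 = 28.4.

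**2. The two effect sizes.** For two equal groups, eta squared = d²/(d² + 4) = .04/4.04 = .0099, about 1%. Conversely, 2% gives d = 2·√(.02/.98) = .286.

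**3. Trying to reproduce 0.90 with d = .2 as the group difference.**

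*Two-group contrast at one visit.* L = N·d²/4 = 3.00 / 2.27, df 1 and N − 2: power 0.41 / 0.32. With d = .286 it is 0.69 / 0.57.

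*Group main effect.* L = (N/4)·m²·3/(1 + 2r), df 1 and N − 2, where m is the mean difference over the three visits. Power is highest at r = 0.
- d = .2 at all three visits (m = .2): at r = 0, L = 9.00 / 6.81 and power is 0.849 / 0.738. At r = .5 it is 0.561 / 0.451.
- Section 25.3's pattern of 0, .2, .2 (m = .133): at r = 0, L = 4.00 / 3.03 and power is 0.513 / 0.410.

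*Group x Time, pattern 0, .2, .2.* L = (N/4)·Σ(difference − m)²/(1 − r), df 2 and 2(N − 2). The sum is 2(.04)/3 = .0267, so L = 2.00/(1 − r) / 1.51/(1 − r).

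| r | Group x Time | Group, same pattern |
|---|---|---|
| .3 | 0.306 / 0.240 | 0.351 / 0.278 |
| .5 | 0.414 / 0.322 | 0.291 / 0.232 |
| .8 | 0.813 / 0.689 | 0.235 / 0.189 |

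Group x Time reaches 0.90 at r of about .84 / .88. A higher correlation helps Group x Time and hurts Group, so no r ≥ 0 brings both to 0.90 at d = .2.

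**4. Readings that favour the plan.** If the stated effect is entered as the interaction effect itself, L = 3N·f²/(1 − r). For the pattern 0, d, d, f² = (2d²/3)/12 = d²/18.
- d = .2 entered as f = .1: Group x Time has 0.974 / 0.919 at r = .5. The implied follow-up difference is √(18 × .01) = .42. Group at that difference has 0.849 / 0.738 at r = .5. At 227, Group needs r of .14 or less and Group x Time .47 or more, so they never both pass 0.90. At 300 both pass only for r of about .29 to .35.
- Eta squared 2% (f² = .02/.98 = .0204): Group x Time has 0.976 / 0.924 at r = 0, and Group has 0.963 / 0.902 at r = .8. Both pass 0.90 at both sample sizes for r up to .8. The implied follow-up difference is √(18 × .0204) = .61.

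**5. The section 25.3 rule.** If the true d is .2, the observed d falls below .20 about half the time. The chance of a declared effect is therefore capped near one half, whatever the power to reject the null. By simulation at 227 (pattern 0, .2, .2; r from .3 to .8), rejecting Group x Time and also observing d ≥ .20 has probability 0.17 to 0.37 if d is the mean follow-up difference, or 0.23 to 0.50 if it is the difference in change.

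**6. Aim 2.** For a 1-df term, L = n·r²/(1 − r²), where r² is the partial r². At .04 to .06, power in the full 227 is 0.86 to 0.97. On half of 300 (n = 150), .04 gives 0.70; on half of 227 (n = 113) it gives 0.58. The section does not say which term or n its .70 refers to.

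**The case against.** The strongest defence is that section 25.1 offers two effect sizes, and the second can support the claim. Eta squared 2%, read as the interaction effect, puts both planned tests above 0.90 at both sample sizes for correlations up to .8. That stands. A reader might infer that nothing stated in section 25.1 can yield 0.90, or that no Aim 1 test can reach it; the documents support neither. Group x Time can also pass at d = .2 with a correlation of about .84 (N = 300) or .88 (N = 227). The ceiling of 0.85 / 0.74 applies to the Group main effect with d = .2 as the between-group difference. A one-sided test at correlation 0 would give 0.91 at 300, but the planned F test is non-directional.

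This does not rescue the sentence. The favourable reading implies a follow-up difference of .61, about three times the d = .2 that the section presents as its equivalent, and nothing tells the reader to adopt it.

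It is also fair to say that 300 is attached to Aim 2, and that the Aim 1 sentence says only that our N suffices. Applying 300 to Aim 1 is an inference, but it is the only N in the section, and the actual target of 227 gives lower power. The 874 in section 9.1 is no alternative, since the same section describes it as the number contacted.

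Finally, a reader might infer that the Aim 2 power of .70 is wrong. That is not shown: it depends on an unnamed term and holds on some readings at 227.

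**Conclusion.** Wrong as written. The conflict between 300 (37 per cell) and 227 (about 28 per cell) needs no statistical assumption. The power statement equates two effects, one about twice the other in variance explained. For a between-group difference of d = .2 it is not met by the Group main effect, which has at most 0.85 at 300 and 0.74 at 227, or 0.51 and 0.41 with no baseline difference. Group x Time has 0.31 to 0.81 at 300 and 0.24 to 0.69 at 227. So with 227 patients and a true d = .2 at both follow-ups, Group x Time would fail to reject 31% to 76% of the time, against the less than 10% that the SAP implies.

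These figures rest on the assumptions listed in the working. The correlation range is assumed, because the documents give none. Attrition, or clustering by provider within one clinic per arm, would be expected to lower power further. The defensible conclusion is that 0.90 does not hold for Group at d = .2 and cannot be reproduced without inputs that the section leaves out.

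**What to change.** Wording changes in section 25.1 only:

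- Replace 300 and 37 with 227 and about 28.
- Keep one effect size, and say whether it is the difference at each follow-up or the interaction effect itself.
- Withdraw the claim of power above 0.90 for d = .2. State alpha, and give power at 227 separately for Group and Group x Time over a range of assumed correlations, using the authors' pilot values if they have them. For d = .2 at both follow-ups, none at baseline and no loss, the figures are 0.24 to 0.69 for Group x Time and 0.28 to 0.19 for Group as the correlation goes from .3 to .8.
- Say that these are probabilities of rejecting the null only, that the observed-d rule in section 25.3 makes the chance of a declared effect lower, and that they assume independent patients.
- Compute the effect of attrition under the EM or FIML handling planned in section 25.2, or label complete-case figures as such.
- Recompute the Aim 2 figure of .70 at 227 and name the term it refers to.

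The cost is a less favourable stated power. No patients, visits or analyses are added.
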